### 6.1 *Toxicity and Adverse Events*

Treatment-emergent adverse events (TEAEs) are any adverse event aggravated in severity from baseline or having their onset between the first dose of the study drug and 31-day ( $\pm 10$  days) after the last treatment dose, death or date of further therapy, whichever came first. AEs related to the study treatment or with unknown relationship occurring more than 31 days after the last dose were also taken into account as TEAEs.

Summary of overall AEs will be done by system organ class (SOC) and preferred term (PT), by severity (worst toxicity grade) and by relationship to the study drug (any of them or both). Tables will be sorted by category of events using SOC (i.e. alphabetic order) and PT in descending frequencies (i.e. from higher to lower).

AEs, SAEs, deaths, laboratory evaluations, dose delays/omissions/reductions and study drug discontinuations due to AEs will be tabulated in a descriptive way. Counts and percentages will be used for categorical variables, and summary tables will be used for continuous variables.

Patients having any treatment-related grade  $\geq 3$  AEs should have relevant tests reassessed at least every 72 hours until recovery to at least grade 2.

### 6.2 *Clinical Laboratory Evaluation*

Laboratory results will be classified according to the NCI-CTCAE v.5. All laboratory visits reported as “End of treatment” visit will be mapped to the last cycle visit for each patient.

The following hematological values will be displayed: white blood cells count (WBC), neutrophil count, lymphocyte count, monocyte count, erythrocytes, hemoglobin, hematocrit and platelet count. Worst grade per patient and per cycle for anaemia, lymphopenia, neutropenia, leukopenia and thrombocytopenia during treatment will be shown.

Overall cross tabulation will be presented for the worst grade during treatment vs. the baseline toxicity grading of anaemia, lymphopenia, neutropenia, leukopenia and thrombocytopenia.

If a grade 3/4 neutropenia or thrombocytopenia increase occurs during a treatment cycle, the first day the onset value is reached (counting from the start of the cycle) will be tabulated. Time to recovery of the abnormality (i.e., grade 3/4 neutropenia or thrombocytopenia) will be assessed and defined as the time, in days, from the start of the grade 3/4 abnormality until the abnormality is recovered (grade  $\leq 2$ ). The analysis will be carried out taking into account all events, including those that occur in a same cycle. The information will be shown by means of median and range.

Likewise, the following biochemical and coagulation values will be displayed: aspartate aminotransferase (AST), alanine aminotransferase (ALT), lactate dehydrogenase (LDH), creatinine, creatinine clearance, glucose, creatine phosphokinase (CPK), CPK-MB fraction, gamma glutamyltransferase (GGT), total bilirubin, direct bilirubin, serum electrolytes (Na+, K+, Mg++, Ca++), total proteins, albumin, C-reactive protein count (CRP) and the international normalized ratio (INR). Worst grade per patient and per cycle for applicable values during treatment will be shown.

Time to recovery of the abnormality (grade 3/4 AST or ALT) will be assessed and defined as the time, in days, from the start of the grade 3/4 abnormality until recovery to grade  $\leq 2$ . The analysis will be carried out taking into account all events, including those that occur in a same cycle. The information will be shown by means of median and range.

Overall cross tabulation will be presented for the worst grade during treatment vs. the baseline toxicity grading of biochemical abnormalities.

### ***6.3 Physical Examination, Vital signs, Left Ventricular Ejection Fraction and Electrocardiogram Findings***

Summary tables will be prepared with the performance status, physical examination, body weight and BSA, vital signs, left ventricular ejection fraction (LVEF) and electrocardiogram (ECG) abnormalities. If appropriate, a “change from baseline” summary will also be done.

ECG will be collected in triplicate allowing rhythm definition (at least 30 seconds of duration), PR interval and QT interval (raw and corrected by HR using Bazett’s formula). Mean of all ECGs collected on each time point will be used for analysis.

### ***6.4 Deaths and other Serious Adverse Events***

Serious adverse events (SAEs) will be tabulated following the same pattern than AEs. Reason of death will be tabulated. In addition, all deaths within 60 days from the first dose of treatment or within 30 days from the last dose of treatment will be listed.

## **7 OTHER ANALYSES**

Continuous variables will be tabulated and presented with summary statistics (i.e., mean, StD, median and range).

Categorical variables will be summarized in frequency tables by means of counts and percentages. Percentages in the summary tables will be rounded and may therefore not always add up to exactly 100%.

## **7.1 Patient Disposition and Treatment/Study Discontinuation**

The number of patients included in the study, the number of patients treated and the number of patients evaluable for the main endpoint will be shown. Also, accrual by center and the main dates of the study will be displayed. Reasons for treatment discontinuation and for study discontinuation will be tabulated.

## **7.2 Protocol Deviations**

Protocol deviations will be listed and categorized according to the following categories:

- Inclusion/exclusion criteria not met
- Incorrect treatment, dose or schedule received
- Excluded concomitant medication received
- Withdrawal criteria met, but treatment continued
- Failure to comply study procedures
- Any other Ethical/GCP issues

In addition, they will be classified as Relevant/Non-relevant according to clinical criteria.

## **7.3 Baseline and Demographic Data**

Baseline data such as demographics, cancer history, prior therapy, prior relevant history, signs and symptoms, electrocardiogram, LVEF, physical examination, vital signs, laboratory values and concomitant medication, coded according to the World Health Organization (WHO) Anatomical Therapeutic Chemical (ATC) classification system, will be described following standard tables detailed in Appendix I.

Age, baseline weight, height and BSA values will be summarized descriptively. Age categories, sex, race and baseline ECOG PS score will be summarized with frequency counts.

For the cancer history, time from initial diagnosis, time from metastatic disease, time from locally advanced disease and time from last progression before the study entry will be summarized. This time calculations will be shown in months and summarized descriptively. Tumor type and other characteristics of the primary and current disease will be described using standard tables detailed in Appendix I.

Previous relevant medical history (other than cancer) will be listed.

A frequency tabulation of the number of patients with the different types of previous surgery, radiotherapy or therapy (number of lines) will be given.

Signs and symptoms will be displayed by tabulation of frequencies according to NCI-CTCAE v.5 toxicity grades. Signs and symptoms will be listed.

In case of pre-treatment characteristics with multiple measurements per subject before the start of treatment (e.g. laboratory assessments or vital signs), the last value prior to or on the first day of treatment will be considered the baseline measurement.

## **7.4 Treatment Administration**

Exposure to treatment will be described by sequence treatment group.

Total cumulative dose, time on treatment, dose intensity and relative dose intensity, administration delay and dose reductions/omissions will be described following standard

tables (detailed in Section 11, Appendix II). The reported cycle information on the case report form (CRF) pages will be used for the analysis.

Time on treatment, expressed in weeks, is defined as the last administration date of lurbinectedin minus the first administration date of lurbinectedin plus 31 days, except if the patient dies or starts a new antitumor therapy within 31 days from the last administration date, in which case the time on treatment will be the date of death or the start date of the new antitumor therapy minus the date of the first administration of the study treatment.

Total cumulative dose by drug, expressed in mg for both lurbinectedin and itraconazole, is the sum of all the product doses received during the study, including the dose received in the last cycle.

For lurbinectedin, intended dose intensity is the planned dose per cycle divided by the planned number of weeks by cycle.

Absolute dose intensity is the actual cumulative dose divided by the number of weeks of treatment. As a convention, for this calculation, the duration of the last cycle will be the predefined cycle length (e.g, 21 days). Relative dose intensity (%) is the ratio of absolute dose intensity divided by the intended dose intensity. In those cases where the relative dose intensity is over 100% due to permitted dose anticipation (i.e. patients receiving more dose than planned), this ratio will be adjusted to 100%.

The options “Dose Reduced” and “Dose Delayed” available in the Treatment Modification item on the treatment exposure CRF pages will be used to calculate delays and dose reductions, respectively. For cycles considered as delayed by the Investigator, the length of the delay will be calculated as:

Duration of cycle delay: Date of the current drug administration – Date of the previous drug administration – the predefined cycle length (i.e., 21 days).

For itraconazole, the percentage of compliance will be calculated by dividing the actual total dose by the intended dose.

If the number of delays or dose reductions are very low, tables will not be presented and only listings will be shown.

### **7.5 Subsequent Therapies**

A listing of the first subsequent therapies received after treatment discontinuation will be shown by study part and treatment sequence group.

### **7.6 Imputation in Incomplete Dates**

Dates of certain historical or current clinical activities are key component for statistical analysis. An incomplete date results from a missing day, month or year; in that case, the missing figure can be imputed allowing for the calculation of variables, such duration and time to certain event. However, when all of them, day, month and year, are missing no imputation will be done.

Before randomization/treatment start date

All variables needed to summarize for example prior information (e.g. first diagnosis date) where partial information is available will be subject of imputation by means of SAS programming. If the day of a date is unknown then the imputed day will be 1, if the month is also unknown then the imputed date will 1/July. This assumption will be valid if the imputed date is earlier than the randomization date; otherwise, the imputed date will be the first day of the month of the randomization date (i.e. 01/Randomization month date/year).

#### Between treatment start and end of treatment

All date variables during treatment where information is needed and is not fully available, for example adverse events or concomitant medications, will be subject of imputation by means of SAS programming. If the day of a date is unknown then the imputed day will be 1, if the month and/or year is also unknown then the imputed date will 1/January (this assumption will be valid if the imputed date is not earlier than the treatment start date; otherwise, the imputed date will be the treatment start date).

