## 2 OVERALL STUDY DESIGN

This is a prospective, open-label, two-way crossover, phase Ib drug-drug interaction study in patients with advanced solid tumors.

The study will include a pre-treatment (screening) phase (within 14 days before the first lurbinectedin or itraconazole administration) followed by a treatment phase consisting of two lurbinectedin cycles, one cycle in combination with itraconazole and one cycle of lurbinectedin as single agent (in different order depending on the study sequence), and one additional third cycle of lurbinectedin as a single agent for patients who meet the continuation criteria and obtain a clinical benefit after the first two cycles, and then follow-up of adverse events if any.

Patients who meet the continuation criteria and obtain a clinical benefit according to the Investigator's criteria will have the opportunity to continue treatment under a Compassionate Use Agreement after the completion of the optional third study cycle.

[figure not shown]
Patients will be treated as outpatients. At the discretion of the Investigator, patients may be admitted to the study center on Day -1 or Day 1 and monitored, at least, until completion of the Day 1 PK blood sample collections.

Patients will receive a maximum of three cycles: two consecutive cycles of lurbinectedin, one cycle with and one cycle without itraconazole co-administration (in different order depending on the study Sequence 1 or Sequence 2 of treatment), followed by a third cycle with lurbinectedin alone (this last optional for patients with clinical benefit). Lurbinectedin will be administered as a 1-hour (-5/+20 min) i.v. infusion q3wk via a central or peripheral vein.

In the co-administration cycles, itraconazole will be administered orally once daily in the morning after breakfast during 12 consecutive days, self-administered at home from Day -4 (i.e., four days before lurbinectedin infusion) until Day 8 (i.e., seven days after lurbinectedin infusion), and supplied at the study center on Day 1, following recommendations at the Summary of Product Characteristics (SmPC). On Day 1 (i.e., the day of lurbinectedin infusion), itraconazole will be given immediately prior to starting the lurbinectedin infusion. In fact, itraconazole should be administered after obtain the itraconazole PK sample #1 and before the start of lurbinectedin infusion (-15 min to -1 min).

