## 11.2 Adverse Events (AEs)

This analysis will be carried out on evaluable patients for the safety population.

All adverse events tables will be listed by study part and sequence and differentiating by treatment (Test, Reference or both). Additional groups could be done (such as PM01183 alone or in combination) if required, and a sequential number will be added at the end of the table number.

AEs consisting of laboratory abnormalities (e.g., neutropenia) may be under-reported as AEs. Since these events are better evaluated using objective laboratory results, laboratory abnormalities will be discussed in Section 11.4.

The type of toxicity and worst grade or severity by cycle and by patient will be summarized according to System Organ Class (SOC) and Preferred Term (PT) as per the MedDRA dictionary. Subsequent grouping of similar or clinically related items might be appropriate at the time of the analysis. Tables will be organized by category of events using SOC and PT. Grades could be presented by separate or any other grouping at the time of the analysis.

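### Setting partial on-treatment dates to day 1 of the month, with treatment start as the only lower limit, can date Cycle 2 events in the other treatment's cycle and end dates before onset

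*SAP*

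**What the plan says.** SAP 7.6 has three date rules. The one for the interval between treatment start and end of treatment covers "All date variables during treatment where information is needed and is not fully available, for example adverse events or concomitant medications". For these, "If the day of a date is unknown then the imputed day will be 1"; where the month or year is missing too, the date becomes 1 January. The result stands unless it falls before treatment start; "otherwise, the imputed date will be the treatment start date". The rule does not separate onset from end dates, set a lower limit at the start of a cycle, or require an end date to fall on or after onset. The section gives its purpose as "allowing for the calculation of variables, such duration and time to certain event".

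SAP section 2 gives each patient one cycle with itraconazole and one without, in an order set by sequence. SAP 7.4 takes a cycle as 21 days. On the reporting side, SAP 11.2 states: "All adverse events tables will be listed by study part and sequence and differentiating by treatment (Test, Reference or both"). The SAE tables (11.3.1) follow the same layout, and the concomitant-medication tables (11.7.1) also have T and R columns. Section 11.5 plans, if applicable, a generalized linear mixed model comparing severe events between the combination and lurbinectedin alone.

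**The concern.** In a parallel-group trial, moving an onset back to the first of the month leaves the patient in the same arm. Here the cycle determines the treatment, so a backward shift of days can change the column in which an event belongs. For Cycle 2 records the shift runs from Reference to Test in sequence TR, which includes all of Part A, and from Test to Reference in RT. The effect of itraconazole on lurbinectedin's safety profile is a stated secondary objective, and the T/R tables are its main output. In so small a trial, one misplaced grade 3/4 event is visible in a cell.

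The second problem concerns end dates. Setting a missing end day to the first of the month is the earliest choice available, and it can produce an event that ends before it begins.

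**Working it through.** The plan gives no figure on this point, so there is none to reproduce.

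**Inputs.** From the SAP: the day-1 rule and its lower limit (7.6), the 21-day cycle (7.4), itraconazole from Day -4 (section 2), the nadir in the middle of the second week (section 1), and the 31-day (±10) window after last dose (6.1). From protocol 9.2: three patients in Part A, all TR, and eight in Part B randomized 1:1. Assumed: onsets are uniform over the window considered, and the mean month is 365.25/12 = 30.4375 days.

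**Onset dates.** Suppose an event starts on day U of Cycle 2. Its imputed date stays in Cycle 2 only if a first-of-month falls within days 1 to U, which has probability U/30.4375. So P(dated before Cycle 2) = 1 - mean(U)/30.4375. The limit at treatment start does not help, because treatment start precedes Cycle 2.

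The check column enumerates real calendar dates, using every Cycle 1 Day 1 over four years.

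| Case | Formula | Calendar check |
|---|---|---|
| Cycle 2, days 1-21 | 1 - 11/30.4375 = 63.9% | 63.9% |
| Days 8-15, around the nadir | 1 - 11.5/30.4375 = 62.2% | 62.2% |
| RT Test period from Day -4 (25 days) | 1 - 13/30.4375 = 57.3% | 57.3% |
| Cycle 2 last, onsets over 31 days | 47.5% (U capped at one month) | 47.5% |
| Cycle 2 last, onsets over 41 days | not computed | 35.9% |
| Day and month missing, days 1-21 | 1 - 11/365.25 = 97.0% | 97.0% |

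Delaying Cycle 2 by 7 or 14 days leaves the first figure at 63.9% and 63.8%.

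The shift is only backwards, so a Cycle 1 event cannot move into Cycle 2. Planned numbers are 3 + 8/2 = 7 TR and 8/2 = 4 RT, so the two directions need not cancel. One qualification: the optional Cycle 3 is lurbinectedin alone, so a Cycle 3 onset dated back into Cycle 2 would go from Reference to Test in RT and would keep its treatment in TR.

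**End dates.** Take a known onset, uniform over the 42 days of Cycles 1 and 2, a true duration of L days, and a missing end day. The imputed end precedes onset when no first-of-month falls in the L + 1 days from onset to end, except for an onset on treatment start itself (1 of 42 days). So P = (41/42) × (1 - (L + 1)/30.4375):

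- L = 0: 94%
- L = 3: 85%
- L = 7: 72%
- L = 14: 50%
- L = 21: 27%

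Calendar enumeration gives the same values.

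**Illustration with invented dates.** Cycle 1 Day 1 is 20 May, so Cycle 2 Day 1 is 10 June. An onset on 18 June with its day missing becomes 1 June, which is Cycle 1 Day 13. If the onset is known and the true end is 25 June with its day missing, the end also becomes 1 June, 17 days before onset.

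**The case against.** The strongest reply is that no table cell need change. The SAP never says that events are assigned to Test or Reference by imputed date. Listings 11.2.1.10 to 11.2.1.12 carry cycle and treatment beside the start and end dates, and SAP 7.4 says the cycle reported on the CRF will be used for the analysis. If that holds for adverse events, imputation moves nothing between columns. This stands as a condition on the conclusion. It does not remove the point, because the 7.4 sentence concerns treatment administration and no rule is given for adverse events or concomitant medication. SAP 7.12 leaves conventions not in the SAP to a separate document, which might supply an assignment rule; the date rule itself is already fixed in 7.6.

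A reader might infer that the time-to-recovery summaries are also distorted. The documents do not support that: SAP 6.2 and Tables 11.4.3.2 and 11.4.3.4 define them for neutropenia, thrombocytopenia, AST and ALT, which rest on dated laboratory samples. Nor is a planned table shown to report negative durations. The planned adverse event tables are worst-grade counts, and I found none of event duration. The end-date fault therefore shows in listings and in any duration derived later.

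Exposure is also limited. Visits are frequent in both cycles, sites contact patients daily during itraconazole, and about 11 patients are planned. A moved event alters a worst-grade cell only if no other event already fills it. All of this stands and keeps the expected effect small.

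**Conclusion.** The rule as written is unsuitable for this crossover. It dates about 64% of Cycle 2 onsets with a missing day in the other treatment's cycle, assuming uniform onset over 21 days, and it permits end dates before onset. It would be too strong to say that most such events are always misdated: the share is 57% with the RT Test period counted from Day -4, and below half (47.5%) when Cycle 2 is last and onsets spread over 31 days.

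It would also be too strong to say that the T/R tables will be wrong. They are wrong, record by record, only where assignment uses the imputed date, and the SAP leaves that open. In that case the affected outputs are the tables in 11.2.1, 11.3.1 and 11.7.1 and the optional model in 11.5. The number of partial dates is unknown but should be small. The primary PK comparison uses parameters measured by cycle and does not depend on these dates.

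**What to change.** Amend SAP 7.6 and 11.2 as follows.

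- **Assignment:** state that adverse events are assigned to Test or Reference by the cycle recorded on the CRF. State a rule for concomitant medication too; Listing 13.34 already carries the cycle.
- **Missing onset day:** impute the later of day 1 of the month and the start of the recorded cycle's treatment period. For the co-administration cycle that period starts at the first itraconazole dose, and the T/R tables must use the same boundary. Otherwise an RT event dated between Day -4 and Day 1 of Cycle 2 would again fall on the wrong side. Apply the same lower limit when the month is missing.
- **Missing end day:** impute the last day of the month, capped at death or the end of the reporting period, and never before onset. Without the cap, a month-end date could fall after death.

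With these rules no imputed onset precedes its recorded cycle's treatment period and no imputed end precedes onset, provided that the recorded cycle is correct. The cost is a few sentences and minor programming, with no new data collection.

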#### After end of treatment

A conservative approach for the variables collecting information after end of treatment where partial information is available (e.g., follow-up AEs) will be imputed by means of SAS programming. The following rules will be implemented: if the day of a date is unknown then the imputed day will be 1; if the month is also unknown, then the imputed date will be 1/July. This assumption will be valid if the imputed date occurs later than the last drug administration date; otherwise, the imputed date will be the last drug administration date plus 1 day.

